Speech Adaptation When Using Mouthguards

Research Protocol

4 October 2017

Table of content

	Page
Introduction	3
Problem Statement	4
Research Questions	4
Hypothesis	4
Aim and Objectives	5
Methodology	5
Flow Chart of Methodology	11
References	13

1. Introduction

Contact sports are defined as sports in which players interact with each other, trying to prevent the opposing team or player from winning (Barbic et al., 2005). Thus, participation in sports carries a considerable risk for dental injuries (Sane, 1998.) Due to the unavoidable repeated bodily contact, dental trauma highly prevalent among rugby players (Abdullah et al., 2015). The prevalence and severity of sport-related dental injuries varied, with an estimate between 0.2% and 33.5%, but is likely to be underreported (Cohenca et al., 2007). The risk of injuries increased with the age of the players, especially among those involved in long hours of training and compete professionally (Turbeville et al., 2003).

Dental trauma often involves injuries to the tooth structure, periodontal tissue, oral mucosa and temporomandibular joints (Feliciano, 2006). The vulnerable site is the upper jaw, particularly upper incisors (Glendor, 2008). These injuries often affect the appearance of the casualties, causing undue psychological stress (Berger, 2009). Furthermore restoring the injured teeth often requires extensive dental procedure with long-term follow-up at a high cost (Glendor, 2001). Thus, familiarity with the emergency procedure for dental trauma was essential for improving the condition of the affected tooth. However, knowledge of dental trauma prevention and management were generally insufficient, suggesting the need to educate and train the athletes (Abdullah et al., 2015).

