4. Aim and Objectives

The aim of this study is to evaluate the effect of wearing custom-fitted mouthguards on the speech performance and oral impairment of the Malaysia national rugby players.

The specific objectives are :

- i. To compare the speech performance before, immediately after, one-week after, one-month after and six-month after wearing custom-fitted mouthguard;
- ii. To compare the level of oral impairment before, immediately after, one-week after, one-month after, and six-month after wearing custom-fitted mouthguard; and
- iii. To estimate the incidence of traumatic dental injury within the six-month custom-fitted mouthguards use period.

5. Research hypotheses

The null hypotheses are :

- i. Speech performance at various time points is not affected by wearing custom-fitted mouthguard;
- ii. Level of oral impairment at various time points is not affected by wearing custom-fitted mouthguard; and
- iii. No incidence of dental trauma occurs within the six-month custom-fitted mouthguards use period.

6. Methodology

An interventional study using single-arm pre- and post- design will be carried out at the National Sports Institute. All the national rugby players taking part in the Asia Rugby Championship Premier 2018 will be invited to participate in this study. The information sheet regarding the study will be given out while the objectives and conduct of the study will be explained to the players. All players who agreed to participate will need to provide written informed consent.

To be eligible for inclusion, the players must be:

- a) Men aged between 18 and 35;
- b) Actively playing rugby;
- c) Currently playing in Malaysia Rugby Union;
- d) Native speakers of Malay (national language), with the ability to read and write in Malay fluently;
and
- e) Without any history of either speech or hearing impairment.

The exclusion criteria are:

- a) Retired players;
- b) National players who did not play rugby within the last six months of the recruitment date; and
- c) Players with cleft lip and/or cleft palate; and

d) Players with any history of either speech or hearing impairment.

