The sample size was calculated using G*Power 3.1 software (available at <http://www.gpower.hhu.de/>). The assumptions was an effect size of 0.25 with a 5% margin of error. The power of the study 80% and there was a total of six repeated measurements. Correlation among the repeated measures was set at 0.5. This yielded a minimal sample size of 24. Considering that drop-outs are higher with long-term follow-up, the sample size was increased by 20% to $n = 30$.

Development of questionnaire to evaluate oral impairment

A questionnaire will be developed to evaluate any oral impairment that could be experienced by the subjects before and during the use of a mouthguard. The questionnaire will be divided into four parts: (i) demographic information such as gender, age, frequency and duration of playing, highest level of representation and experience wearing custom-fitted mouthguard, (ii) frequency of wearing mouthguard, (iii) problems arise during mouthguard use and (iv) general perception on mouthguard. All questions in part (ii), (iii) and (iv) will be formatted in a five-point Likert scale. The following ratings will be given for the different possible answers in part (ii) and part (iii) with a qualitatively ordinal character: “Never” = 1; “Rarely” = 2; “Sometimes” = 3; “Often” = 4; “Always” = 5. For part (iv), the possible responses were: “Strongly disagree” = 1; “Disagree” = 2; “Neutral” = 3; “Agree” = 4; “Strongly agree” = 5. The questionnaires will be printed in Malay, the national language of Malaysia.

This questionnaire set will be validated and pretested on 10 undergraduate dental students. The cognitive interview will be carried out while the students are completing the questionnaire. Face validity will be determined as the degree to which they agree that the items of the questionnaire are appropriate and adequate to measure pattern and problems of wearing the mouthguard, as well as the general perception on the mouthguard.

Fabrication of mouthguards

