Prior to the fitting of the mouthguard, speech samples will be recorded from each participant. These speech samples were used as control (T₀). The recording of speech samples will be performed using the Sony IC Recorder (ICD-SX700/SX800, San Diego, USA) in a quiet room to minimize background sound. The recorder will be placed 15 cm away from the player's lips and each player will be asked to read loudly a list of selected Malay words (*paku* for phoneme /p/, *bola* for phoneme /b/, *tatu* for phoneme /t/, and *dadu* for phoneme /d/), as the words are shown one after another on the computer screen. Each session will take about 10-20 minutes to complete. Three recordings will be obtained for each word. The mouthguard will then be fitted for each player. The recording of speech samples will be repeated immediately following wear (T₁), and at the following intervals: one-week after (T₂), one-month after (T₃) and six-month after wear (T₄).

Evaluation of oral impairment and compliance

Before the mouthguard is fitted, all participants will be asked to fill up the questionnaires (at T₀). They will also be requested to fill up the same questionnaire at the same time points prior to the recording of the speech samples at T₁, T₂, T₃, and T₄.

Compliance and injury monitoring

Throughout the six-month period, the compliance of wearing mouthguards and the occurrence of dental trauma during training will be monitored on-site by the researcher or if not available, an assigned coach. A 24-hour helpline will be provided as a surveillance tool to monitor problems with mouthguards and dental trauma. Besides, replacement mouthguard will be provided for only once, if the players damage or misplace the mouthguard. However, if the players damage or misplace the mouthguard more than two times, they will be withdrawn from the research.

Data analysis

Data collected from the questionnaires will be analyzed using SPSS version 23.0 (IBM Corporation, Armonk, NY, USA). Descriptive analysis will be performed for demographic data to have an overview of the participants' age, frequency, and duration of playing and experience of wearing a custom-fitted mouthguard.

[figure not shown]

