For the self-assessment questionnaire of oral impairment, Friedman's test will be used to test for differences between groups because the dependent variable being measured is ordinal. Statistical significance is set at $\alpha = 0.05$. Subsequently, the Wilcoxon signed-rank test will be used for pairwise comparison. Bonferroni adjustment will be done to correct for multiple testing. For part (ii) self-reported frequency of wearing custom-fitted mouthguards, comparisons will be made between T₂, T₃, and T₄. Hence, the adjusted level of statistical significance is set at $\alpha = 0.05/3 = 0.017$. For (iii) problems arise during mouthguard use, and (iv) general perception on a mouthguard, the level of statistical significance is adjusted to $\alpha = 0.05/6 = 0.008$ because of multiple testing between T₁, T₂, T₃, and T₄.

All the recorded speech waveforms will be digitized (at a sampling rate of 22 kHz and 32-bit resolution) and stored on a compact disk. The speech samples collected will be transcribed into the PRAAT software version to assess the acoustic characteristics of the sound via spectrographic analysis. Each speech sample file was given a number which referred to a participant's profile to blind the assessor.

By using spectrogram analysis, mean voice onset time (VOT) values for all phonemes */p b t d /* will be measured in a millisecond. The measurements will be done by manually positioning two cursors in the display of the waveform/spectrogram in the sample file. The beginning and end of a particular measurement of a sound will be judged from both the waveform and spectrogram. The average mean VOT values and voicing duration from the three readings will be obtained for each phoneme.

One-way repeated-measures analysis of variance (ANOVA) will be used to compare the VOT of each phoneme at different time intervals (T_0 , T_1 , T_2 , T_3 , T_4). Statistical significance is set at $\alpha = 0.05$.

7. Flowchart of the study

6 month monitoring period

1. Monitoring logbook
2. 24-hour helpline
3. Modification/replacement of mouthguards (if necessary)

Fourth Speech Performance Recording (T₃)

Fourth Questionnaire Oral Impairment Survey
(T₃)

8. References

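### On-site observation of dental injury is worded for training only, while objective (iii) covers every setting, so match injuries may be under-counted

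*Combined protocol and SAP*

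**What the plan says.** Section 4 of the protocol gives the third objective as "To estimate the incidence of traumatic dental injury within the six-month custom-fitted mouthguards use period". Neither it nor research question (iii) in Section 3 distinguishes training from matches.

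Section 6 invites national players competing in the Asia Rugby Championship Premier 2018, and one inclusion criterion is "Actively playing rugby".

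Three sources of injury information are named:

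- **On-site observation** (Section 6, Compliance and injury monitoring): "the occurrence of dental trauma during training will be monitored on-site by the researcher or if not available, an assigned coach".
- **Helpline** (same paragraph): "A 24-hour helpline will be provided as a surveillance tool to monitor problems with mouthguards and dental trauma".
- **Logbook** (Section 7, flowchart): the entry "Monitoring logbook" is listed for the six-month monitoring period. The flowchart is only partly readable in the public text, and the readable text does not describe the logbook's contents.

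The oral-impairment questionnaire is repeated at T0 to T4. Section 6 says of its format: "All questions in part (ii), (iii) and (iv) will be formatted in a five-point Likert scale". Part (iii) concerns problems during mouthguard use, and no dental-injury item is described.

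**The concern.** The quantity to be estimated and the way its events are found do not have the same scope. The objective counts every dental injury in six months, whereas the one source in which somebody is on the spot looking for injuries is tied to training. A researcher or substitute coach could follow the monitoring paragraph to the letter and never record anything at a match.

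If match injuries reach the dataset less reliably than training injuries, the six-month incidence is too low, and a reader cannot tell by how much. The direction matters because Section 2 suggests that the protective effect of the custom-fitted mouthguard could be evaluated from this study. An under-count would favour the device.

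**Working it through.** The plan gives no expected incidence, capture rate or precision target for objective (iii), so there is no figure of its own to reproduce. The check sets the scope of each source against the objective and then shows what incomplete match capture would do.

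**Step 1. Scope of each source**

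| Source | Settings covered as worded | Does someone actively look for injuries? |
|---|---|---|
| Objective (iii) | All | (target) |
| On-site researcher or coach | Training | Yes |
| 24-hour helpline | All | No; needs a call |
| Monitoring logbook | Not stated in the readable text | Not stated in the readable text |
| Questionnaire, part (iii) | Not stated; items still to be written | Asked of every player, but as a Never-to-Always rating, which gives no count, date or setting |

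No source is described as actively seeking match injuries.

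**Step 2. Effect on the incidence**

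Let m be the share of injuries that occur in matches and c the fraction of those that is captured. Assume that training injuries are captured completely. Then

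recorded / true = (1 − m) + m × c = 1 − m(1 − c).

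Neither m nor c is in the documents, so both are assumed:

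| | c = 50% | c = 80% | c = 100% |
|---|---|---|---|
| m = 25% | 0.875 | 0.95 | 1.00 |
| m = 50% | 0.75 | 0.90 | 1.00 |
| m = 75% | 0.625 | 0.85 | 1.00 |

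For example, m = c = 50% gives 1 − 0.5 × 0.5 = 0.75.

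**Step 3. Scale in a study of this size**

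Take the planned n = 30, an assumed true six-month risk of 10%, and at most one injury per player.

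- Expected injured players: 30 × 0.10 = 3.
- Expected recorded at m = c = 50%: 3 × 0.75 = 2.25, a recorded risk of 7.5%.
- Chance of recording no injury at all: 0.90^30 = 4.2% with full capture, and 0.925^30 = 9.6% at a recorded risk of 7.5%.
- Exact (Clopper-Pearson) 95% interval for 3/30: 2.1% to 26.5%. For 0/30: 0 to 11.6%.

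In this example the loss is under one player, which is small beside the sampling uncertainty. A confidence interval does not reflect the under-count, however, so a wide interval does not remove the problem.

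**The case against.** The strongest reply is that match injuries are already under surveillance. The helpline has no limit of setting, and the logbook is listed for the whole monitoring period. Observers who see about 30 players at training throughout the six months could learn of a match injury at the next session. The reference to training may also be loose wording for all rugby activity. Much of this stands: match injuries are not excluded, and capture could be complete. What remains is that no readable passage says anyone seeks them, and both the helpline and later discovery depend on an injury being mentioned or noticed.

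Several stronger readings are tempting, but the documents do not support them.

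- *That the plan has no match surveillance, or that the logbook omits matches.* The flowchart is incomplete in the public text, so the logbook may well cover matches.
- *That the protocol admits under-reporting in this study.* The words "but is likely to be underreported" in the Introduction describe published prevalence, not a monitored cohort.
- *That early withdrawals will bias the result.* This depends on the denominator, and the readable analysis text specifies no incidence estimator.
- *That the null hypothesis "No incidence of dental trauma occurs within the six-month custom-fitted mouthguards use period" defeats the objective.* It can be read as a statement about what is observed in this cohort, and the objective already calls for estimation.

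The documents give no match dates, so the amount of match play within the six months is also unknown.

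**Conclusion.** The point holds as a mismatch of scope: the objective covers all settings, and the described on-site observation covers training. If match capture is less complete than training capture, the incidence is biased downwards. The size cannot be obtained from the documents. Under the assumed values in the table, recorded incidence runs from 0.625 of the true value to no loss at all. Those figures rest on complete training capture and on values of m and c that are assumptions.

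Severity is minor. Injury incidence is the third of three objectives, the study is small, and the speech and questionnaire comparisons do not depend on it.

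**What to change.** 1. At the existing T2, T3 and T4 visits, ask every player whether any dental injury has occurred since the last visit, in training or in a match. Record yes/no, number, date and setting.
2. State in the monitoring paragraph that on-site and logbook recording covers matches as well as training. If the logbook already does so, one sentence is enough.
3. If match recording is not feasible, restrict objective (iii) and research question (iii) to injuries in training.
4. Report the incidence with an exact 95% confidence interval, together with the number of players not followed to six months.

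The cost is one extra question at three planned visits and a few lines of protocol text. The main drawback is recall. The T4 question reaches back to T3, from six months to one month, which is about five months. The question therefore supplements the logbook and does not replace it.

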Mouthguards are typically composed of a thermoplastic copolymer, designed to fit over the occlusal surfaces of the maxillary teeth and extending near to the vestibular reflection (Patrick et al., 2005). Several authors demonstrated that wearing a mouthguard during sport can reduce the occurrence and severity of dental trauma (Yesil et al., 2009). Therefore, some sports authorities mandate the use of mouthguard (Quarrie et al., 2005). The purpose of using a mouthguard is to act as a buffer from trauma and provide a degree of protection for both the mouth's soft tissues (lips, gums, tongue) and hard tissues (teeth and alveolar bone) as well as protection from brain injuries (Knapik et al., 2007). The ability to protect the mouth is highly dependent on the ability of the mouthguard in shock absorption and impact dissipation (Craig et al., 2002).

There are basically three types of mouthguards that are available in the market. Type I (stock) are sold to the public and are used without any modification. Type II ('boil and bite') mouthguards are the most commonly used mouthguards on the market and represent 90% of all mouthguards worn (Padilla et al., 1996). These are made of a thermoplastic material that is softened and then molded to the dental arch by the user. Type III (custom-made) are made by a dentist using a mold of the patient's dental arches (Barbic et al., 2005).

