Rugby is contact sports that need good physical fitness skills and specific skills depending on the position played. The team that can quickly and efficiently communicate during a rugby game has a clear advantage. Thus, building good on-field communication habits make much easier for rugby players to work together. However, if the communication fails during rugby games, the prospect of success in offense and defense during rugby games will be greatly decreased (Gordon, 2005). Among Malaysian university rugby players, those who discontinued using mouthguard complaint that general discomfort and speech disturbance are the main barriers to compliance (Liew et al., 2014). The nuisance is largely due to their use of poorly-fitted stock or boil-and-bite mouthguards (Liew et al., 2014). In comparison, custom-fitted mouthguards were considered the best choice because of its ability to maintaining oral moistness and adaptation, hence causing less interference with respiration and speech, while improving comfort and limiting nauseating effect (Duarte-Pereira et al., 2008). However, limited availability and higher prices hinder its widespread use (Guevara et al., 2001).

To date, the intensity and duration of oral discomfort caused by mouthguard remain unclear, with no published study to evaluate speech performance that employed acoustic analysis and sonography. Hence, the aim of this research is to evaluate the impact of wearing mouthguards on the speech performance of the athletes.

2. Problem Statement

Rugby exposes players to increased risk of dental trauma. Thus, mouthguard use is often recommended. However, a mouthguard can affect speech. It is unclear to what extent speech performance improve over time.

Therefore, this project is intended to evaluate the impact of wearing mouthguards on the speech performance of the players. In addition, the effectiveness of custom-fitted mouthguards in the prevention of dental trauma could be evaluated.

3. Research Question

- i. Is there any difference in speech performances before (at baseline), immediately after, one-week after, one-month after and six-month after wearing a custom-fitted mouthguard?
- ii. Is there any difference in the level of oral impairment immediately after, one-week after, one-month after and six-month after wearing a custom-fitted mouthguard?
- iii. What is the incidence of traumatic dental injury among rugby players during the six-month period of wearing a custom-fitted mouthguard?

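### Players who damage or lose the guard more than twice leave the whole study, so injury and wear follow-up ends for a reason plausibly related to both

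*Combined protocol and SAP*

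**What the plan says.** The rule is in section 6 (Methodology), under Compliance and injury monitoring: "However, if the players damage or misplace the mouthguard more than two times, they will be withdrawn from the research". The sentence before it limits supply: "replacement mouthguard will be provided for only once, if the players damage or misplace the mouthguard".

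The same paragraph sets the intended follow-up: "Throughout the six-month period, the compliance of wearing mouthguards and the occurrence of dental trauma during training will be monitored on-site". A helpline runs alongside, and the flowchart (section 7) adds a monitoring logbook.

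Three other places depend on that follow-up being complete:

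- Objective iii (section 4): "To estimate the incidence of traumatic dental injury within the six-month custom-fitted mouthguards use period".
- The questionnaire schedule for T1 to T4 (section 6, Evaluation of oral impairment and compliance): "They will also be requested to fill up the same questionnaire at the same time points prior to the recording of the speech samples".
- The wear analysis (section 6, Data analysis): "For part (ii) self-reported frequency of wearing custom-fitted mouthguards, comparisons will be made between" T2, T3 and T4.

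The protocol does not define an analysis set, a missing-data method, or person-time or censoring for the incidence. It does not say how a withdrawn player is counted.

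**The concern.** The rule turns an event that happens during guard use into an exit from the study. Read literally, a player who meets it is no longer watched for injury, asked how often he wears a guard, or given the T4 questionnaire.

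The trigger is unlikely to be unrelated to what is measured. The Introduction states that "wearing a mouthguard during sport can reduce the occurrence and severity of dental trauma". On that premise, players left without a guard would be at higher risk, and they are the ones no longer observed. Someone who repeatedly loses a guard may also be an infrequent wearer, and frequency of wear is what part (ii) records.

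Two results are exposed: the injury incidence over six months, and the wear comparisons that involve T4. The injury count is likely to be small in a sample of 30, and the third null hypothesis (section 5) is that no dental trauma occurs at all. One unobserved injury could therefore change that conclusion.

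**Working it through.** The documents give no rate of loss, damage or injury, so there is no plan figure for this bias to reproduce, and its actual size cannot be computed. The one related figure is the drop-out allowance: 24/(1 − 0.20) = 30, which is room to lose 6 players. It protects power; it does not protect against selective loss.

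**Inputs.** From the protocol: 30 players and six months of follow-up, so 30 × 6 = 180 player-months. Assumed: 3 players withdrawn at month 3; injury rate r per player-month in the other 27 and k·r in these 3.

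**Step 1: injuries missed, k = 3.**
- Expected in all 30: 27×6×r + 3×6×3r = 162r + 54r = 216r.
- Missed after month 3: 3×3×3r = 27r.
- Share of injuries missed: 27/216 = 12.5%.
- Share of follow-up lost: 3×3/180 = 9/180 = 5%.

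**Step 2: bias in the rate, k = 3.**
- Full follow-up: 216r/180 = 1.20r.
- With withdrawal: (216r − 27r)/(180 − 9) = 189r/171 = 1.105r.
- Ratio: 1.105/1.20 = 0.921, so about 8% too low.

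**Step 3: dependence on k.** In general the full rate is r(162 + 18k)/180 = r[1 + (k − 1)/10]. The observed rate is r(162 + 9k)/171 = r[1 + (k − 1)/19].

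| k | full | observed | bias |
|---|---|---|---|
| 3 | 1.20r | 1.105r | about −8% |
| 2 | 1.10r | 1.053r | about −4% |
| 1 | r | r | none |

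For k below 1 the sign reverses and the observed rate is too high.

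**Step 4: incidence as a proportion.** Suppose 1 injury is seen among the 27 who stay: 1/27 = 3.7%. For all 30, the figure lies between 1/30 = 3.3% (none of the 3 injured) and 4/30 = 13.3% (all 3 injured). The protocol does not say which denominator applies.

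**Step 5: how many players reach the trigger.** Assume loss or damage events are Poisson with mean m per player over six months, ignoring the supply limit. The expected number of 30 players with three or more events is 30 × [1 − e^(−m)(1 + m + m²/2)]. This gives 0.06 at m = 0.25, 0.4 at m = 0.5, 2.4 at m = 1 and 5.7 at m = 1.5. Three players by month 3 is therefore a fairly demanding assumption.

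**Step 6: wear.** T2 and T3 fall at one week and one month, so a withdrawal at month 3 removes only the T4 answer. Friedman's test uses complete rows, so that player's T2 and T3 answers also drop out of the omnibus test. He drops out of the paired tests that involve T4 as well. No size is put on this bias, because the documents say nothing about wear in such players.

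**The case against.** The strongest reply is that the rule may hardly ever operate. One loss brings a replacement, and no second replacement is provided. A third event then needs a guard that was repaired, found or obtained elsewhere. This stands: impact is uncertain, and a reader should not infer that any single loss removes a player. It also exposes a contradiction, because the status of a player after a second loss is undefined.

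Second, objective iii is worded around the period of guard use, so injuries after use ends arguably fall outside it. That is a legitimate reading. It still needs time on guard to be defined, which the protocol does not do. Reporting by guard status and for all enrolled players serves either reading.

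Third, the link to outcomes is inferred. Damage could come from frequent wear, that is, from good compliance, and the bias could then run the other way. This stands. A reader might infer that those withdrawn are known to do worse; the documents do not show it.

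A reader might also infer that impairment in part (iii) is understated. The documents do not support that. The Introduction says "those who discontinued using mouthguard complaint that general discomfort and speech disturbance are the main barriers to compliance", which ties discomfort to stopping use, not to loss or damage. Part (iii) also asks about problems while a guard is worn, so a player without one has no score to recover.

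Finally, after a guard is gone, a part (ii) answer reflects supply as well as willingness to wear it. That is a reason to record whether a guard was available, not a reason to stop asking.

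**Conclusion.** The point holds in a limited form. The rule ends data collection, not only guard use, and the plan neither recovers nor accounts for what is then missing. That can bias the six-month injury incidence and the part (ii) comparisons involving T4. No claim is made about part (iii).

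The size is illustrative only. With 3 of 30 withdrawn at month 3 and three times the injury rate, the rate per player-month is about 8% too low. The 12.5% is the share of injuries missed and should not be read as the bias in the rate. If r were 10%/6 per player-month (assumed), the missed 27r would be 0.45 of an injury. With equal rates the rate per player-month is unbiased, though 5% of follow-up is still lost.

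The case for change rests less on the size than on two facts: lost follow-up cannot be recovered by analysis, and preventing the loss costs little.

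**What to change.** Reword the sentence so that meeting the loss or damage criterion does not end data collection. Unless the player withdraws consent:

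- continue injury monitoring to month six through the existing logbook and helpline;
- continue the remaining questionnaires, with part (ii) recording actual wear and part (iii) completed only if a guard is worn;
- make guard-in speech recordings only if a guard is available.

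In Data analysis, state that injury incidence will be reported by time with and without the guard, and for all enrolled players over six months. Record the dates on which a player had no guard so that this time can be calculated.

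The sponsor must reconcile the replacement limit with the withdrawal trigger, including what applies after a second loss. No rule on re-supply or on stopping guard use is proposed here.

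The cost is one reworded sentence and a short addition to the analysis section. The visits, logbook and helpline already exist. A few more questionnaires must be collected, and compliance may look slightly worse.

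### Within each questionnaire item, Holm's step-down rule would recover a little power at no cost compared with the fixed cut-offs of 0.017 and 0.008

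*Combined protocol and SAP*

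**What the plan says.** Section 6, Data analysis, sets out the questionnaire analysis in two stages. First, "Friedman's test will be used to test for differences between groups because the dependent variable being measured is ordinal". Then: "Statistical significance is set at $\alpha = 0.05$. Subsequently, the Wilcoxon signed-rank test will be used for pairwise comparison", with a Bonferroni adjustment.

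- Part (ii), frequency of wear: "comparisons will be made between T₂, T₃, and T₄". "Hence, the adjusted level of statistical significance is set at" 0.05/3 = 0.017 for each pair.
- Parts (iii) and (iv), problems and perception: "the level of statistical significance is adjusted to $\alpha = 0.05/6 = 0.008$ because of multiple testing between" T1, T2, T3 and T4.

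The plan does not say that pairs are tested only when Friedman is significant, and it does not list the visits that enter Friedman. The questionnaire is also completed at T0 (Evaluation of oral impairment and compliance). Objective ii in section 4 includes the visit before fitting; research question ii in section 3 does not.

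The only power statement is in the sample-size paragraph of section 6: "The power of the study 80% and there was a total of six repeated measurements", with effect size 0.25 and correlation 0.5. It names no outcome and no pairwise comparison.

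**The concern.** Objective ii asks how impairment compares across visits, and the pairwise tests are what locate a change in time. A single fixed level applies the strictest threshold to every pair, even after other pairs have been rejected. With 24 to 30 players, that gives up power that could be kept with no loss of error control. A non-significant pair may then be misread as no change or full adaptation, the more so if the reader takes the 80% to apply to each pair.

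**Working it through.** **The plan's own figures.** Three visits give 3 pairs and 0.05/3 = 0.01667; four visits give 6 pairs and 0.05/6 = 0.00833. Both match the printed levels after rounding. As printed, 3 × 0.017 = 0.051 and 6 × 0.008 = 0.048, so unrounded levels are cleaner. The minimum of 24 is reproduced by a multivariate repeated-measures F test with six measurements, f = 0.25 and correlation 0.5 (power 0.825), and 24/0.8 = 30. That is an omnibus calculation. It uses six measurements where the plan has five time points, T0 to T4.

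**Why Holm costs nothing.** Order the m p-values and compare the j-th smallest with 0.05/(m − j + 1), stopping at the first failure.

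- Three pairs: 0.05/3, 0.05/2, 0.05.
- Six pairs: 0.05/6, 0.05/5, 0.05/4, 0.05/3, 0.05/2, 0.05.

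No step is below 0.05/m, so every pair rejected at 0.05/m is also rejected by Holm. If m0 nulls are true, a false rejection requires the smallest of their p-values to be at most 0.05/m0. The chance of that is at most m0 × 0.05/m0 = 0.05. Neither a gate nor any link between the nulls is needed. If a Friedman gate is applied as well, it can only remove rejections.

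**Size of the gain.** The documents give no effect size, distribution or correlation for the questionnaire. The runs below assume f = 0.25 over the compared visits and correlation 0.5. Average power per truly different pair, without a gate:

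| Visits, n, data | Pattern | Bonferroni | Holm | Gain |
|---|---|---|---|---|
| 4, 24, continuous | two extremes, two in the middle | 0.231 | 0.253 | 0.022 |
| 4, 24, continuous | linear | 0.197 | 0.217 | 0.020 |
| 4, 30, continuous | two extremes, two in the middle | 0.299 | 0.340 | 0.041 |
| 3, 24, continuous | linear | 0.305 | 0.339 | 0.034 |
| 3, 30, five-point | linear | 0.336 | 0.373 | 0.037 |
| 3, 30, five-point | first visit differs | 0.533 | 0.569 | 0.036 |

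Five-point items over four visits gave gains of about the same size. When no visit differs, simulated familywise error without a gate was 0.028 to 0.040. It is the same for both rules there, because they share the first step.

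**The larger, conditional gain.** Suppose Friedman at 0.05 is a true gate on exactly the compared visits, and the nulls are equal distributions across visits. Once three visits are not all equal, at most one pair can be equal, so each pair can be tested at 0.05. With four visits at most three pairs can be equal, so the divisors become 3, 3, 3, 3, 2, 1 (Shaffer). Average power against the planned levels with the same gate:

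| Visits | n | Planned, gated | Gated Shaffer |
|---|---|---|---|
| 4 | 24 | 0.15–0.33 | 0.22–0.45 |
| 4 | 30 | 0.22–0.48 | 0.28–0.59 |
| 3 | 24 | 0.24–0.39 | 0.34–0.51 |
| 3 | 30 | 0.32–0.51 | 0.43–0.63 |

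The gain is about 6 to 13 points, with familywise error 0.012 to 0.049. If T0 enters the gate and only T0 differs, the gate opens while every later null is true. Familywise error then reached about 0.06 to 0.07 (four later visits) or 0.11 to 0.125 (three).

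**What the 80% does not cover.** With correlation 0.5 the SD of a difference is √(2 × (1 − 0.5)) = 1 in units of the visit SD. For f = 0.25 over four visits, the widest difference lies between 2 × 0.25 = 0.50 (two visits against two) and √8 × 0.25 = 0.71 (two extremes). Power for that pair at 0.05/6, from a paired noncentral t with Wilcoxon efficiency 3/π:

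- n = 24: 0.33 to 0.68.
- n = 30: 0.44 to 0.81.
- Smaller steps of 0.25 to 0.35: 0.06 to 0.14 at n = 24, and 0.08 to 0.19 at n = 30.

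On five-point items the widest pattern gave 0.55 at n = 24 and 0.72 at n = 30.

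**The case against.** Bonferroni after Friedman is prespecified, simple and safe whichever visits enter Friedman, so preferring another rule can look like taste. That defence holds against the gated rule. The plan states no gate, T0 data exist, and a guard newly in the mouth may well change answers relative to T0. The reduced divisors also need linked nulls, which signed-rank tests of paired differences do not strictly guarantee. If the pairs were meant to be ungated, adding a gate can lose findings: on continuous data at n = 24, the chance of at least one true finding was 0.71 with ungated Bonferroni against 0.67 with gated Shaffer (four visits), and 0.66 against 0.60 (three). The defence does not hold against Holm, which carries none of these conditions.

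A reader might infer three stronger points, and the documents support none of them:

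- **That the plan pays for multiplicity twice.** This presumes a gate that the plan does not state.
- **That the tests miss a promised 80% power.** The sample-size paragraph ties 80% to no pairwise or questionnaire test. Nor does it tie it to voice onset time, so it cannot be relabelled as the power of that analysis.
- **That error is over-controlled in the study as a whole.** The conservatism is per item. Nothing adjusts across items or parts, and neither Holm nor Shaffer would change that.

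**Conclusion.** This is a free improvement, not a flaw in validity. Within an item the fixed levels control error but give up about 2 to 4 points of average power that Holm keeps. Holm's error guarantee and its dominance over Bonferroni at 0.05/m are exact. The one trivial exception is a p-value between 0.01667 and the printed 0.017. The size of the gain rests on assumed patterns, f = 0.25, correlation 0.5 and 24 to 30 players. The further gain from a gated Shaffer rule is real only under the stated conditions. Pairwise power is mostly below 80% under any of these rules, though in the most favourable continuous case one pair reaches about 0.81 at n = 30.

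**What to change.** In Data analysis, replace the two fixed levels with text such as: *Within each item, pairwise Wilcoxon p-values are tested by Holm's step-down procedure at a familywise level of 0.05, using unrounded levels. For part (ii) (T2, T3, T4) the ordered p-values are compared with 0.05/3, 0.05/2 and 0.05. For parts (iii) and (iv) (T1 to T4) they are compared with 0.05/6, 0.05/5, 0.05/4, 0.05/3, 0.05/2 and 0.05. Testing stops at the first failure.* State also which visits enter each Friedman test and whether the pairs depend on its result.

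Use the gated Shaffer rule only if the plan says that pairs are tested solely after a significant Friedman test on exactly T2 to T4 for part (ii) and T1 to T4 for parts (iii) and (iv), without T0, and that the nulls are equal distributions across those visits.

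In the sample-size paragraph, say which outcome and test the 80% refers to, and that it does not cover pairwise questionnaire tests.

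The cost is a few sentences; no new data or tests are needed. Bonferroni's one practical advantage, simple matching simultaneous intervals, is not lost, because the plan specifies no such intervals for the questionnaire.
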